### ***Phase 1-Dose Escalation-Specific Inclusion Criteria***

1. Meeting the Inclusion Criteria for any of the Phase 2 Expansion Cohorts listed below.

### ***Phase 2-Cohort Expansion Specific Inclusion Criteria***

Cohort 1: ccRCC - Checkpoint inhibitor naïve

1. Histological or cytological diagnosis of RCC with a clear cell component.
2. Must have received at least one but not more than two prior anti-angiogenic therapy regimens in the advanced or metastatic setting.
3. Must have received no more than three total prior systemic treatment regimens in the advanced or metastatic setting.

Cohort 2: ccRCC - Nivolumab in most recent line of therapy (“add-on”)

1. Histological or cytological diagnosis of RCC with a clear cell component.
2. Received nivolumab in the immediate prior line of therapy with  $\leq 8$  weeks elapsed between last dose of nivolumab and C1D1 of the CX-839-004 study and EITHER:
  - a) Had documented radiological disease progression (per Investigator assessment, preferably with confirmation of PD after 4 weeks), OR

- b) Had documented stable disease (per Investigator assessment) for  $\geq 24$  weeks.

Cohort 3: ccRCC - Any prior anti-PD-1/ PD-L1

1. Histological or cytological diagnosis of RCC with a clear cell component.
2. Received an active anti-PD-1 or anti-PD-L1 agent and achieved no better than SD prior to demonstrating radiological progression (per Investigator assessment) in any prior line of therapy. An active anti-PD-1 or anti-PD-L1 agent is defined as an agent that has demonstrated clear evidence of single agent activity, e.g., nivolumab, pembrolizumab, atezolizumab, durvalumab, or avelumab. Any other anti-PD-1 or anti-PD-L1 agent need approval from the Medical Monitor.
3. Must have received at least one prior anti-angiogenic therapy regimen in the advanced or metastatic setting.

Cohort 4: Melanoma (progressing while on anti-PD-1/PD-L1 therapy)

1. Histological or cytological diagnosis of advanced/metastatic melanoma.
2. Received anti-PD-1/PD-L1 as monotherapy or as part of a combination regimen in the most recent line of therapy with (i) documented radiographic disease progression (per Investigator assessment, preferably with confirmation of progression after 4 weeks) and (ii)  $\leq 8$  weeks elapsed between last dose of anti-PD-1/PD-L1 and C1D1 of the CX-839-004 trial.
3. Previously progressed on or was intolerant to BRAFi therapy if BRAF V600E mutation is present.

Cohort 5: NSCLC (anti-PD-1/PD-L1 in most recent line of therapy (“add-on”))

1. Histological or cytological diagnosis of NSCLC that does not harbor an activating EGFR or ALK mutation.
2. Received anti-PD-1/PD-L1 agent as the most recent line of therapy with  $\leq 8$  weeks elapsed between last dose of anti-PD-1/PD-L1 therapy and C1D1 of the CX-839-004 trial and EITHER:
  - a) Had documented radiological disease progression (per Investigator assessment, preferably with confirmation of PD after 4 weeks), OR
  - b) Had documented stable disease (per Investigator assessment) for  $\geq 24$  weeks.

Cohort 6: Melanoma (to be treated with CB-839 monotherapy)

1. Histological or cytological diagnosis of advanced/metastatic melanoma without curative options.
2. At least 4 mo (approximately 5 half-lives) elapsed between most recent dose of anti-PD-1/PD-L1 therapy and C1D1 of CB-839 monotherapy.
3. Previously progressed on or was intolerant to BRAFi therapy if BRAF V600E mutation is present.

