#### **6.3.2.2 Cohort 2: ccRCC patients with disease progression or prolonged SD ( $\geq 24$ weeks) while receiving nivolumab in their most recent line of therapy**

This cohort will enroll ccRCC patients that received nivolumab in their most recent line of therapy with minimal washout ( $\leq 8$  weeks), with the intent of adding CB-839 to the ongoing nivolumab regimen. Since this patient population has either documented radiological disease progression OR long-term SD ( $\geq 24$  weeks), the likelihood of a response on nivolumab monotherapy is extremely low and any activity can be confidently attributed to the addition of

CB-839. The primary endpoints of Cohort 2 will be safety/tolerability, ORR, and DOR per Investigator. Predose and postdose biopsies will be collected during Stage 1 in order to demonstrate a pharmacodynamic effect of CB-839 in the context of PD-1 inhibition by nivolumab and correlate efficacy with potential predictive biomarkers (Section 14.2).

Since the mechanisms of resistance to nivolumab may be different in the settings of primary refractory disease, relapsed, and long-term stable disease, patients in Cohort 2 will fall into one of the following subgroups:

- a) Patients with progressive disease after achieving no better than SD
- b) Patients with progressive disease after achieving an objective response
- c) Patients with SD as their best response for  $\geq 24$  weeks

A Simon's two-stage design will test the null hypothesis that the ORR  $\leq 0.05$  versus the alternative that ORR  $\geq 0.15$ ; the sample size of 56 patients will maintain an alpha level of 0.10 and a power of 0.80. If at least 2 patients respond (PR or better) out of 20 response-evaluable patients in Stage 1, then an additional 36 evaluable patients will be enrolled in Stage 2 (total of 56 response-evaluable patients). If Stages 1 and 2 are completed, a minimum of 5 patients must demonstrate a response (PR or better) to reject the null hypothesis. The lower target ORR (15%) is based on the heterogeneity of histological subtypes (with potentially differential sensitivity to CB-839) in this cohort.

Of note, up to 5 additional patients may be enrolled in Stage 1 in order to ensure sufficient enrollment of each of the subgroups. Based on emerging data, the Sponsor may choose to restrict further enrollment in this cohort to one or two of the three subgroups identified above.

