#### **6.3.2.4 Cohort 4: Melanoma patients with disease progression while receiving an anti-PD-1 therapy in their most recent line of therapy**

This cohort will enroll melanoma patients with radiological disease progression (per Investigator assessment) while receiving an anti-PD-1/PD-L1 agent as monotherapy or in a combination regimen to treat advanced/metastatic melanoma in the most recent line of therapy. There must be  $\leq 8$  weeks elapsed between last dose of anti-PD-1/PD-L1 and C1D1 of the CX-839-004 trial. The intent of this cohort is to convert progressing disease to responding disease by the addition of CB-839 to ongoing anti-PD-1/PD-L1 therapy. Because this patient population has documented disease progression on anti-PD-1/PD-L1 therapy at study start, the likelihood of a response to nivolumab monotherapy is extremely low and any activity can be confidently attributed to the addition of CB-839. Patients on anti-PD-1/PD-L1 agent other than nivolumab will switch to nivolumab for treatment on this study. The primary endpoints of Cohort 4 will be ORR and DOR as determined by an Independent Radiology Committee (IRC). Pre- and post-dose biopsies will be collected from all patients enrolled into the Expansion phase of Cohort 4 (so long as deemed safe and technically feasible to biopsy) in order to demonstrate a pharmacodynamic effect of CB-839 in the context of PD-1 inhibition and to correlate efficacy with potential predictive biomarkers ([Section 14.2](#)).

The original study design with 24 patients tested the null hypothesis that ORR of CB-839 + nivolumab was  $\leq 5\%$  versus the alternative of  $\geq 20\%$  with an alpha level of 0.1 and power of

80%. Per study design, 9 patients would be enrolled in Stage 1 and 1 responder would trigger enrollment of an additional 15 patients in Stage 2; while 3 responders out of 24 total patients would lead to formal rejection of the null hypothesis. To date there have been 3 responding patients (including one complete response and 2 deep partial responses of -73% and -47%), all confirmed responses on repeat scan  $\geq 4$  weeks after initial response, in 16 evaluable patients. Notably, per protocol eligibility, all of these patients were experiencing disease progression on PD-1/PD-L1 inhibitor therapy in the immediate prior line of therapy strongly suggesting that the response was the result of the addition of CB-839.

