**6.5 Exclusion Criteria**

1. Intolerance to prior anti-PD-1/PD-L1 therapy including 1) discontinuation due to immune-related toxicity or, 2) immune-related toxicities that required intensive or prolonged immunosuppression (including high-dose IV corticosteroids, > 2 mo of immunosuppressive corticosteroids (i.e., equivalent of >10mg oral prednisone daily) or the addition of potent immunosuppression to corticosteroids (e.g., mycophenolate mofetil/CellCept or infliximab) to manage.
  - Exception: Cohort 6 patients are eligible to receive CB-839 monotherapy (but not combination with nivolumab) even if prior intolerance of anti-PD-1/PD-L1 therapy.
2. Prior severe hypersensitivity reaction to another monoclonal antibody (mAb).
3. Any other current or previous malignancy within the past three years except a) adequately treated basal cell or squamous cell skin cancer, b) carcinoma *in situ* of the cervix, c) prostate cancer with stable prostate specific antigen (PSA) levels for 3 years, d) or other neoplasm that, in the opinion of the Principal Investigator and with the agreement of the Medical Monitor, will not interfere with study-specific endpoints.
4. Cytotoxic chemotherapy, tyrosine kinase inhibitor (or other targeted anti-cancer agent), radiation therapy, or hormonal therapy within 14 days or 5 half-lives, whichever is longer, prior to Cycle 1 Day 1 (42 days for nitrosoureas or mitomycin C).
5. Immunotherapy or biological therapy (e.g., monoclonal antibodies) within 21 days prior to Cycle 1 Day 1.
  - EXCEPTION: Washout of anti-PD-1 therapy is NOT required in Expansion Cohorts 2, 4, and 5 and must be > 4 mo in Expansion Cohort 6.
6. Treatment with an unapproved investigational therapeutic agent within 21 days (or 5 half-lives for small molecule agents) prior to Cycle 1 Day 1.
7. Any active known or suspected autoimmune disease.

Permitted on Study	
 
• Vitiligo
 
• type I diabetes mellitus
 
• residual hypothyroidism due to autoimmune condition only requiring hormone replacement
 
• psoriasis not requiring systemic treatment for 2 years
 
• conditions not expected to recur in the absence of an external trigger
 

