**6.6 Radiological Tumor Assessments**

All patients will be evaluated for tumor response assessed by Investigator according to both RECIST version 1.1 and modified RECIST for immune-based therapeutics (termed iRECIST) (Seymour 2017). The primary study endpoints of response rate and duration of response will be determined according to RECIST v1.1 by Investigator assessment except for Cohort 4 which will employ IRC adjudication for the primary endpoints. *In contrast to the formal study endpoints, patient management and clinical decision making during treatment should follow the principles and guidelines for iRECIST (Attachment 5).* These criteria take into account the observation that some patients with solid tumors can have an apparent radiographic flare of disease on immunotherapy that is transient and followed by radiographic disease response. If imaging shows progressive disease per RECIST v1.1 (unconfirmed PD per iRECIST), it is recommended to keep the patient on study treatment until imaging is repeated  $\geq 4$  weeks later in order to confirm PD, as described in the iRECIST recommendations (see Attachment 5). Patients who are deemed clinically unstable or are experiencing rapid progression of disease are not required to have repeat imaging for confirmation of PD. At a minimum, patients must meet the following criteria for continued treatment on study after disease progression is identified at a tumor assessment:

- Absence of symptoms and signs (including worsening of laboratory values) indicating disease progression
- No decline in ECOG performance status
- Absence of rapid progression of disease or of tumor progression at critical anatomical sites (e.g., cord compression) requiring urgent alternative medical intervention.

If repeat imaging confirms PD as described in [Attachment 5](#), patients will be discontinued from study therapy. If repeat imaging does not confirm PD, treatment with study drugs will continue and the next imaging studies will be conducted every 8 weeks as previously scheduled. In patients who discontinue study therapy early without documented disease progression, every effort should be made to continue monitoring disease status by radiologic imaging until progressive disease, death, withdrawal of consent, or initiation of new anticancer therapy.

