### 10.1 Screening Evaluation

The following screening assessments must be performed **within 28 days** before study drug administration on C1D1 according to the [Schedule of Study Assessments](#). Procedures listed below that are performed as part of the normal standard of care and within 28 days prior to C1D1 may be used for screening purposes:

- Sign and date an IRB/IEC-approved Informed Consent Form (ICF) before any study-specific (i.e., non-standard of care) screening procedures are performed
- Demographic information including date of birth, sex, and ethnic origin
- Medical history including review of prior cancer treatments
- Review of concomitant medications
- ECOG performance evaluation
- Complete physical examination including weight (kg) and height (cm)
- Vital signs and weight

- Standard 12-lead ECG with corrected QT interval by Fridericia's Formula (QTcF)
- Clinical laboratory evaluation (hematology, coagulation, serum chemistry, and urinalysis); see [Attachment 3](#).
- Serum or urine pregnancy test. This is only required for females of child-bearing potential and must be negative within 3 days prior to C1D1
- During Phase 1- Dose escalation, predose and postdose tumor biopsies will be collected from patients enrolled in the back-fill cohorts. Predose tumor biopsies will be obtained from all patients in the Expansion phase (if considered safe and technically feasible to biopsy). Refer to [Section 14.2](#).
- Coagulation tests must be performed and evaluated within 72 to 24 hr prior to all biopsy procedures. Patients in all other cohorts may consent to an optional tumor biopsy.
- Archival tumors, if available, will be collected from all patients
- Screening radiographic evaluation of tumor burden (e.g., diagnostic CT or MRI). For this study, radiographic evaluation of baseline and subsequent tumor burden must be based on a diagnostic, contrast enhanced, CT or MRI (See [Attachment 1 for details and exceptions](#)). All scans from the immediate prior line of therapy will be requested for Cohorts 2, 4, and 5.

#### Screening Evaluation Specific to Cohort 4

- Cohort 4 patients must have a baseline radiographic tumor assessment (methodology as per screening imaging described above) within 7 days prior to C1D1 unless the patient has had a previous radiographic tumor assessment that meets the following requirements:
  - a. It was performed within 4 weeks of C1D1 **AND**

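### Cohorts 2, 4 and 5 can enrol patients whose prior progression on anti-PD-1 was unconfirmed or had not persisted, and the SAP has no analysis that separates them

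*Protocol*

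**What the plan says.** **Entry criteria.** Protocol 6.4 gives Cohorts 2 and 5 the same progression criterion (2a): "Had documented radiological disease progression (per Investigator assessment, preferably with confirmation of PD after 4 weeks), OR" stable disease of at least 24 weeks (2b). Cohort 4 criterion 2(i) asks for "documented radiographic disease progression (per Investigator assessment, preferably with confirmation of progression after 4 weeks)" in the most recent line. The 8-week limit runs from the last anti-PD-1 dose to C1D1, not from the scan that showed progression. No criterion in 6.4 or 6.5 says what later scans must show.

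**Continuity of the prior drug.** Protocol 6.5 states: "Washout of anti-PD-1 therapy is NOT required in Expansion Cohorts 2, 4, and 5". Section 8.1 lets these patients stay on anti-PD-1 until 3 weeks before C1D1, and all then receive nivolumab on study.

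**Premise.** Section 6.3.2.4 justifies Cohort 4 with "Because this patient population has documented disease progression on anti-PD-1/PD-L1 therapy at study start". Section 6.3.2.2 says of Cohort 2 that "the likelihood of a response on nivolumab monotherapy is extremely low and any activity can be confidently attributed to the addition of" CB-839. Sections 6.3.2.4 and 6.3.2.5 make the same claim for Cohorts 4 and 5.

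**Flare.** Section 6.6 accepts that "some patients with solid tumors can have an apparent radiographic flare of disease on immunotherapy that is transient and followed by radiographic disease response" and recommends treating through a first progression on study until it is confirmed.

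**Partial safeguards.** Section 10.1 sets the timing of the Cohort 4 baseline scan but no required finding. Section 16.4.3.1 defines a Melanoma Confirmed PD Population (progression confirmed more than 4 weeks after its first date in the prior line), but 16.5 assigns it no analysis. SAP 7.1 does not contain the set, and SAP 7.7 does not list its removal.

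**The concern.** These are single-arm cohorts with no control. A response is read as a CB-839 effect only because continued anti-PD-1 alone is presumed to produce almost none. For the progression route, that presumption depends on the progression being real and still present when CB-839 starts. The entry text does not secure this, and the protocol's own account of flare describes how it can fail: a first progression on anti-PD-1, treatment through it, then shrinkage on the same drug class.

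Any such patient raises the response rate with no contribution from CB-839. Cohorts 2 and 5 are sensitive to this because only 5 responders in 56 reject the null. As the SAP stands, a reader of the ORR table could not tell whether responders came from patients with confirmed prior progression.

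**Working it through.** **1. Reproduce the plan's figures.** Inputs are from Protocol 6.3.2.2, 6.3.2.5 and Table 22.2-1: n1 = 20, r1 = 1, n = 56, r = 4, p0 = 0.05, p1 = 0.15.

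P(reject | p) = sum over x from 2 to 20 of P[Bin(20, p) = x] × P[Bin(36, p) > 4 − x].

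- At p = 0.05: 0.0967 (plan: 0.10)
- At p = 0.15: 0.801 (plan: 0.80)

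For Cohort 4 (6.3.2.4, 16.3), the Clopper-Pearson 95% interval named in SAP 7.4.1 gives 10.6% to 29.3% for 14/75, which excludes 10%. For 13/75 the lower limit is 9.6%, which does not. At a true rate of 10%, the chance of at least 14/75 is 0.016, or 0.014 if at least one response in the first 9 patients is also required (Table 22.2-1). The design arithmetic is sound; the question concerns the background rate put into it.

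**2. Assumed model.** Neither of these inputs is in the documents:

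- f = share of the cohort whose prior progression was transient or did not persist
- q = their chance of a confirmed response from study baseline on continued anti-PD-1

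Everyone else responds at the background rate b (0.05 in Cohorts 2 and 5, 0.10 in Cohort 4), and CB-839 adds nothing. The effective null rate is p = b + f(q − b).

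**3. Cohorts 2 and 5**

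| f | q | p | P(reject) |
|---|---|---|---|
| 0 | – | 0.05 | 0.097 |
| 5% | 15% | 0.05 + 0.05 × 0.10 = 0.055 | 0.129 |
| 10% | 20% | 0.05 + 0.10 × 0.15 = 0.065 | 0.203 |
| 20% | 20% | 0.05 + 0.20 × 0.15 = 0.08 | 0.332 |

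**4. Cohort 4, at least 14/75**

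| f | q | p | With stage 1 condition | Without |
|---|---|---|---|---|
| 0 | – | 0.10 | 0.014 | 0.016 |
| 10% | 20% | 0.10 + 0.10 × 0.10 = 0.11 | 0.029 | 0.033 |
| 20% | 20% | 0.10 + 0.20 × 0.10 = 0.12 | 0.054 | 0.061 |

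**5. Sensitivity to q.** With f = 5% and q = 50%, p in Cohorts 2 and 5 is 0.05 + 0.05 × 0.45 = 0.0725 and P(reject) is 0.27. A small share with a high late-response rate therefore matters as much as a larger share with a modest one.

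**The case against.** The strongest reply has five parts.

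- **The intended population is clear.** The Cohort 4 criteria sit under a heading describing patients progressing while on anti-PD-1/PD-L1, 6.3.2.4 places progression at study start, and 6.3.2.2 sorts Cohort 2 into three subgroups, none of which is current shrinkage. This stands as evidence of intent. A reader might infer that the protocol openly accepts patients already shrinking on the prior drug; it does not say so. Their eligibility is inferred from the word preferably and from the lack of any rule on later scans.
- **Prior shrinkage does not score.** Correct. A reader might infer that responses already achieved on the prior drug are counted. RECIST in Attachment 4 measures PR as at least a 30% decrease from study baseline, that baseline is no more than 4 weeks before treatment, and Protocol 16.5 requires confirmation at 4 weeks or later. Shrinkage before baseline lowers the reference sum and makes PR harder. Only a further confirmed decrease counts.
- **The 5% null was not set for progressing patients alone.** Also correct. In Cohorts 2 and 5 it covers progression or stable disease of at least 24 weeks, so non-progressing patients enter by design through 2b.
- **Cohort 4 already has protection.** In part. The recent baseline scan and the Confirmed PD definition make it the least exposed cohort. But the scan need not show anything in particular, the definition implies that unconfirmed patients are enrolled, and the SAP has no such set.
- **The magnitude is assumption.** It is: f and q have no source in the documents. Section 6.3.2.4 also puts the Cohort 4 background below 10%, so starting from a full 10% is conservative for the plan. The highest Cohort 4 figure shown in the tables, 0.061, stays under the 0.10 in Table 22.2-1, though it exceeds the 0.025 per side implied by a 95% interval.

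**Conclusion.** The concern holds in a limited form. The criteria for Cohorts 2, 4 and 5 do not require that progression on the prior anti-PD-1 line be confirmed or still present at C1D1. The design premise assumes that it is, and the SAP has no analysis that would show whether this affects ORR.

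Under the stated assumptions (f 5% to 20%, q 15% to 20%, no CB-839 effect) the false-positive rate in Cohorts 2 and 5 would move from 0.097 to between 0.13 and 0.33. For Cohort 4, with f 10% to 20% and q 20%, the chance of at least 14/75 at a 10% background, with the stage 1 condition, would move from 0.014 to between 0.03 and 0.05. These figures show sensitivity and do not estimate what happened. The documents do not support saying that type I error is in fact inflated by these amounts.

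Tightening eligibility is a tempting remedy but a poor trade. A rule barring any fall in the sum of diameters after the progression scan would exclude patients who truly progressed through new or non-target lesions, and would turn on small measurement differences. The exposure is better handled in the analysis.

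**What to change.** **SAP 7.1.** Restore the Melanoma Confirmed PD Population from Protocol 16.4.3.1, and define the same set for patients who entered Cohorts 2 and 5 by the progression route (2a).

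**SAP 7.4.1.** As a pre-specified sensitivity analysis, report ORR with its Clopper-Pearson interval in that set. Also report it by confirmed versus unconfirmed or non-persisting prior progression. Classify from investigator-assessed prior-line scans, since Protocol 10.1 provides that "All scans from the immediate prior line of therapy will be requested for Cohorts 2, 4, and 5", and from the Cohort 4 baseline scan. Tabulate patients who cannot be classified.

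**SAP 7.7.** Record how the Confirmed PD set is handled relative to the protocol.

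**Protocol text.** Reconcile the study-start wording in 6.3.2.4 with Cohort 4 criterion 2(i), and qualify the attribution statements in 6.3.2.2, 6.3.2.4 and 6.3.2.5.

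**Cost.** One further table and no new imaging. Subsets will be smaller with wider intervals, and some patients will be unclassifiable because prior scans are requested rather than required. In Cohorts 2 and 5 this addresses only the progression route; late responses among patients admitted with prolonged stable disease remain possible and should be acknowledged.

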### **6.3.2.3 Cohort 3: ccRCC patients with disease progression while receiving an anti-PD-1/PD-L1 therapy in any prior line of therapy**

This cohort will enroll ccRCC patients that had documented radiological disease progression while receiving an anti-PD-1/ PD-L1 therapy in any prior line of therapy. An active anti-PD-1/ PD-L1 agent is defined as an agent that has demonstrated evidence of activity, e.g., nivolumab and pembrolizumab, atezolizumab, durvalumab, or avelumab. Since this patient population had documented disease progression on the prior anti-PD-1/ PD-L1 therapy, the likelihood of a response on nivolumab monotherapy is very low and evidence of activity can be confidently

attributed to the addition of CB-839. The primary endpoint of Cohort 3 will be safety/tolerability, investigator assessed ORR, and DOR per Investigator. Predose biopsies will be collected in order to correlate efficacy with potential predictive biomarkers ([Section 14.2](#)).

A Simon's two-stage design will test the null hypothesis that  $ORR \leq 0.05$  versus the alternative that  $ORR \geq 0.2$ ; the sample size of 24 patients will maintain an alpha level of 0.10 and a power of 0.80. At least 9 evaluable patients will be enrolled in Stage 1. If at least 1 patient responds (PR or better) out of 9 response-evaluable patients in Stage 1, then an additional 15 evaluable patients will be enrolled in Stage 2 (total of 24 response-evaluable patients). If Stages 1 and 2 are completed, a minimum of 3 patients must demonstrate a response (PR or better) to reject the null hypothesis.

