***Disease-specific Exclusion Criteria:***

Cohort 1: ccRCC - Checkpoint inhibitor naïve

1. Prior treatment with an anti-PD-1, anti-PD-L1, anti-PD-L2, anti-CD137, or anti-CTLA-4 antibody, or any other antibody or drug specifically targeting checkpoint or T-cell co-stimulation pathways. Prior IL-2 and IFN therapy is allowed.

Cohort 3: ccRCC - Any prior anti-PD-1

1. Patients that achieved an objective response (per investigator assessment) while receiving prior anti-PD-1/PD-L1 therapy.
2. Patients who are eligible for Cohort 2.

Cohort 4: Melanoma

1. Patients with ocular melanoma.
2. Active or untreated CNS metastases.

Cohort 5: NSCLC

1. Documented activating mutation in either the epidermal growth factor receptor (EGFR) or anaplastic lymphoma kinase (ALK).

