  - b. It was performed at least 4 weeks after the date of a prior scan demonstrating progressive disease on anti-PD-1/PD-L1 containing therapy in the immediate prior line of therapy
- Cohort 4 patients must have screening contrast-enhanced MRI of the brain to assess for brain metastases within 28 days before C1D1

A patient who meets all of the inclusion criteria will enter the study. Screen failures must be captured in the electronic data capture (EDC) system.

## 10.2 Cycle 1

Screening urinalysis, serum chemistry, coagulation, and hematology that occurred *within 3 days* prior to C1D1 do not need to be repeated unless a clinically significant change in the interim is suspected.

Patients should be instructed not to eat breakfast prior to their clinic visit on C1D1 and C1D15. On these days, patients will have all predose procedures performed, take their dose of CB-839 with food then receive nivolumab. Note that all predose assessments must be performed prior to nivolumab and CB-839 administration. The 2nd dose of CB-839 will be self-administered by the patient per dosing instructions after all study procedures have been completed.

A detailed breakdown of the visit schedule and sample collection time points can be found in Attachments 1 and 2. During Cycle 1, patients will undergo the following procedures:

- AE Monitoring
- Recording of concomitant medications
- Vital signs and weight
- Symptom-directed physical exam
- ECOG Performance status evaluation
- Clinical laboratory evaluation (hematology, coagulation, serum chemistry, and urinalysis)
- Plasma sample collection for PK and biomarker analysis
- Whole blood sample collection for biomarker analysis
- ECG with QTcF between 2-4 hr post-dose
- Administration of CB-839 and nivolumab

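### Cohort 3's inclusion criterion omits the on-treatment progression that Section 6.3.2.3 uses to define the cohort and to attribute responses to CB-839

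*Protocol*

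**What the plan says.** Protocol Section 6.3.2.3 defines Cohort 3, in its title and its first sentence, by "documented radiological disease progression while receiving an anti-PD-1/ PD-L1 therapy in any prior line of therapy". It then argues that, because these patients had "documented disease progression on the prior anti-PD-1/ PD-L1 therapy, the likelihood of a response on nivolumab monotherapy is very low", activity can be credited to CB-839. The same section sets the null ORR at 5% and the target at 20%, with 9 patients in Stage 1, 24 in total, and at least 3 responses needed to reject the null.

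The Cohort 3 list in Section 6.4 is headed only by prior exposure to an anti-PD-1 or anti-PD-L1 agent. Criterion 2 asks for an active agent and that the patient "achieved no better than SD prior to demonstrating radiological progression (per Investigator assessment) in any prior line of therapy". It gives no timing relative to the last dose.

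Section 10.1 makes the list operative: "A patient who meets all of the inclusion criteria will enter the study".

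**The concern.** Cohort 3 is a single-arm cohort, so eligibility is the only thing that separates a CB-839 effect from a response to nivolumab alone. The design section makes that separation through progression on treatment. The criterion a site would apply does not state it.

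Consider a patient whose best response was SD, who stopped the agent for a reason other than immune toxicity, and who progressed months later off drug. On its wording, criterion 2 is met. That patient does not satisfy the premise of Section 6.3.2.3, yet a response would count towards the 3 needed and be read as CB-839 activity. If such patients respond to nivolumab alone more often than the 5% null allows, the chance of a false positive rises.

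**Working it through.** **1. Does another rule close the gap?**

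- Cohort 3 exclusion 1 (Section 6.5) removes "Patients that achieved an objective response (per investigator assessment) while receiving prior anti-PD-1/PD-L1 therapy". It is silent on when progression occurred.
- General exclusion 1 removes intolerance to the earlier agent, including "discontinuation due to immune-related toxicity" and toxicity that needed intensive or prolonged immunosuppression. Stopping for other reasons is untouched.
- Cohorts 2, 4 and 5 also leave the on-treatment words out of their numbered criteria, although the Cohort 4 list heading includes them. In those three cohorts a limit of 8 weeks from the last dose to C1D1 bounds the gap (Sections 6.4 and 8.1). Cohort 3 has no such limit.
- Cohort 3 excludes anyone eligible for Cohort 2, and the 21-day immunotherapy washout still applies to it. Both move its patients further from their last dose.
- Prior-line scans are requested only for Cohorts 2, 4 and 5 (Section 10.1), so no planned imaging check would show off-treatment progression in Cohort 3.

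The exclusions narrow the route but do not close it.

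**2. Reproduce the stated design.** Inputs (Section 6.3.2.3 and Table 22.2-1): n1 = 9, r1 = 0, n = 24, r2 = 2, p0 = 0.05, p1 = 0.20, one-sided alpha 0.10, power 0.80. With true response rate p,

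P(reject) = Σ over x = 1 to 9 of P(Bin(9, p) = x) × P(Bin(15, p) ≥ 3 − x).

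At p = 0.05:

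- Stage 1: P(0) = 0.95^9 = 0.6302; P(1) = 0.2985; P(2) = 0.0629; P(≥3) = 0.0084.
- Stage 2: P(≥2 of 15) = 0.1710; P(≥1 of 15) = 0.5367.
- P(reject) = 0.2985 × 0.1710 + 0.0629 × 0.5367 + 0.0084 = 0.0510 + 0.0337 + 0.0084 = 0.0931.

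At p = 0.20 the same sum gives 0.8047. The plan's figures reproduce, and the sample-size arithmetic is sound.

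**3. How much slack is there?** The same formula at other values of the nivolumab-alone ORR, with CB-839 adding nothing:

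| Background ORR | P(reject) |
|---|---|
| 5.0% | 0.093 |
| 5.16% | 0.100 |
| 5.5% | 0.115 |
| 6.0% | 0.139 |

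**4. What mix would produce those backgrounds?** Let f be the share of off-treatment progressors and q their nivolumab-alone ORR. Neither is in the documents; both are assumptions. Background = 0.05 × (1 − f) + q × f.

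- f = 10%, q = 10%: 0.045 + 0.010 = 0.055, so P(reject) = 0.115.
- f = 20%, q = 10%: 0.040 + 0.020 = 0.060, so P(reject) = 0.139.
- q = 5% or less at any f: background is at most 5%, so there is no inflation.
- Extreme bound, f = 30%, q = 25%: 0.035 + 0.075 = 0.110, so P(reject) = 0.422. The 25% is the nivolumab ORR that Section 6.3.2.1 cites for checkpoint-naive patients.

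**The case against.** The strongest reply is that the requirement is already in the protocol. Section 6.3.2.3 states it in title and text, and criterion 2's reference to any prior line can be read as progression during that line. On that view there is nothing to fix beyond loose wording. This stands in part: the on-treatment requirement is present in the protocol, and the problem is that two sections disagree. But criterion 2 does not state the on-treatment reading, sites could apply it differently, and Section 10.1 ties entry to the criteria.

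Second, the 5% null is not expressly tied to on-treatment progression. No source is given for it, and Cohorts 2 and 5 use the same 5% while admitting patients with SD of at least 24 weeks who need not have progressed. This stands. What Section 6.3.2.3 does tie to on-treatment progression is the attribution argument.

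Third, the size is assumed. This also stands. A reader might infer that Cohort 3's false-positive rate is in fact inflated, perhaps to 0.3 or 0.4. The documents do not support that. They contain no estimate of f or q and no evidence that off-treatment progressors do better on nivolumab rechallenge. The large figures also apply a checkpoint-naive rate to patients who already failed to respond to an active agent.

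Fourth, the fix is partial and may be late. A patient who progressed on treatment several lines ago would still enter, because any prior line is allowed by design. SAP Section 7.7 says that Cohort 6 was never enrolled, which may mean accrual was near its end, though the documents do not say so for Cohort 3. That is a reason to include a reporting step as well as a wording change.

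**Conclusion.** The inconsistency is established from the text: Section 6.3.2.3 and Section 6.4 criterion 2 describe different Cohort 3 populations, and no exclusion or time limit reconciles them. The argument that responses belong to CB-839 holds only for the narrower population.

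Inflation of the type I error is a possibility, not a finding. It requires that some off-treatment progressors enrol and that they respond to nivolumab alone more often than 5%. If both hold, the rule is sensitive: 0.093 at 5%, crossing 0.10 at about 5.16%, 0.115 at 5.5% and 0.139 at 6%. Crossing 0.10 by a small margin in a non-randomised expansion cohort is modest in itself. Nor should criterion 2 be read as a deliberate decision to admit off-treatment progressors, since Section 6.3.2.3 states the opposite intent.

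**What to change.** Reconcile the two passages. In Cohort 3 inclusion criterion 2, add *while receiving that agent* after the reference to radiological progression, so that the entry rule matches the population Section 6.3.2.3 already states. N, r1 and r2 do not change, and alpha stays at 0.093 if the 5% background holds.

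Record the date of that progression and the date of the last anti-PD-1/PD-L1 dose. Section 8.0 already puts all previous cancer treatments on the eCRF but does not name these two dates.

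For patients already enrolled, report Cohort 3 ORR with and without any off-treatment progressors, as a descriptive addition to SAP Section 7.4.1, which plans no such split.

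The cost is one phrase in an amendment, two dates per patient, one descriptive analysis, and slightly slower accrual if some patients become ineligible.
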